**Scoring:**

Total score: Depression (D) \_\_\_\_\_ Anxiety (A) \_\_\_\_\_

0-7 = Normal

8-10 = Borderline abnormal (borderline case)

11-21 = Abnormal (case)

## APPENDIX 2: Face to Face CST Training Evaluation Questionnaire

Thank you for supporting this research by attending the face-to-face training session(s) run at your workplace. Your involvement and engagement in this professional development training is most appreciated. Please take a few minutes to complete the questions below.

### General Information:

Your professional discipline					Your gender	M	F
Your level of professional experience	< 1 year	1-5 yrs	5-10 yrs	10-20 yrs	20-30 yrs	>30 yrs	
Years of brain injury (stroke/TBI) experience	< 1 year	1-5 yrs	5-10 yrs	10-20 yrs	20-30 yrs	>30 yrs	
Name of your workplace						Date of training	
Names of your presenters							

### Please indicate how this training was presented for you:

As a single 3 hour session?			
As three 1 hour sessions? (Please tick those you attended)	Session 1	Session 2	Session 3

### Please tick the box that best reflects your view of the specific aspects covered in this course:

	Very useful	Quite useful	Neutral	Not very useful	Not at all useful	Other (see below – space for comments)
Knowledge of local cultural issues delivered by a local Aboriginal cultural security trainer						
Explanations of cultural security and how they apply to my workplace						
Explanations of clinical yarning and						

how this can be applied in my workplace						
The use of case scenarios of Aboriginal people with acquired brain injury to support learning						
The opportunity to consider the cognitive, behavioural, and communication impairments which commonly occur after stroke or traumatic brain injury						
The focus on practical strategies, good communication skills, and culturally secure relationships with Aboriginal patients and families						
Experiential learning and the opportunity to reflect on working with Aboriginal patients and families						
Having the time to team-build with colleagues						
Having the time to consider the policies or reconciliation action plan for my workplace						
An opportunity to develop best practice principles in my workplace						

**Please tick the box that best reflects your view of the impact of this course:**

	A lot	A little	Somewhat	Not at all	Other (see below – space for comments)
It has been useful in relation to my team’s work or individual practice					
It will make a difference to the way I work with					

Aboriginal patients and families.						
-----------------------------------	--	--	--	--	--	--

**If you answered *other* or would like to comment further on any aspects of the course, please do so here:**

---

---

---

---

---

---

---

---

---

---

---

---

---

Thank you!

### APPENDIX 3: Online Cultural Security Training Evaluation Questionnaire

Thank you for supporting this research by both attending the previous face-to-face training session(s) run at your workplace and doing the online training (link url). Your involvement and engagement in this professional development training is most appreciated. This questionnaire will focus on your feedback on the online modules and your reflections on this professional development overall. Please take a few minutes to complete the questions below.

#### General Information (complete or circle as appropriate)

Your professional discipline					Your gender	M	F
Your level of professional experience	< 1 year	1-5 yrs	5-10 yrs	10-20 yrs	20-30 yrs	>30 yrs	
Years of brain injury (stroke/TBI) experience	< 1 year	1-5 yrs	5-10 yrs	10-20 yrs	20-30 yrs	>30 yrs	
Name of your workplace							
Approximate time spent completing online modules	1 hour		2 hours		3 hours		
Having time between the face-to-face and online training	Helpful for reflection and applying experiences and information to practice		Neutral		Not helpful for reflection and applying experiences and information to practice		
Access to the site through ECU's HealthInfoNet	Easy access		Difficult to access		Comment:		
Quality of the site developed for this training on ECU's HealthInfoNet	High quality information, presentation and links		Poor quality information, presentation and links		Comment:		
Importance of certificate completion	Very important		Neutral		Not important		

Please tick the box that best reflects your view of the specific aspects covered in the online modules

	Very useful	Quite useful	Neutral	Not very useful	Not at all useful	Other (see below – space for comments)
Section on “learning from my patients”						
The use of case scenarios of Aboriginal people with acquired brain injury to support learning						
	Very useful	Quite useful	Neutral	Not very useful	Not at all useful	Other (see below – space for comments)
Opportunities to view video clips of people’s experiences						
Quiz questions to reinforce learning						
Section on “learning from my colleagues”						
Having scenarios and video clips of people’s experiences						
Practical strategies, and a framework for working with Aboriginal patients and families						
Thinking through practices for: admission, assessment, family involvement, collaborative goal planning, ongoing referrals, discharge planning (please comment more specifically below if you wish).						
Section on “systemic practices”						
Having the time to consider the policies or reconciliation action plan for my workplace						
Following suggested links to other relevant resources						

An opportunity to develop best practice principles in my workplace						
--	--	--	--	--	--	--

**Please tick the box that best reflects your view of the impact of this course**

	Strongly agree	Agree	Neutral	Disagree	Strongly disagree	Other (see below space for comments)
Both the face-to-face and online aspects of this training have been generally useful in relation to my team’s work or individual practice						
This training has made a positive difference to my attitude towards working with Aboriginal patients and families with brain injury.						
This training has made a positive difference to my skills/knowledge in relation to working with Aboriginal patients with brain injury and their families.						
The training was helpful in addressing the specific issues for managing brain injury for Aboriginal patients and families						
This was helpful in promoting stronger working practices with Aboriginal Liaison Officers and/interpreters						
The overall training will make a difference to the way I communicate/yarn with Aboriginal patients and families.						
The overall training will make a difference to the systems in my workplace						

for Aboriginal patients and families.						
---------------------------------------	--	--	--	--	--	--

**If you answered *other* or would like to comment further on any aspects of the course, please do so here:**

\_\_\_\_\_

\_\_\_\_\_

\_\_\_\_\_

\_\_\_\_\_

\_\_\_\_\_

\_\_\_\_\_

\_\_\_\_\_

\_\_\_\_\_

\_\_\_\_\_

\_\_\_\_\_

\_\_\_\_\_

\_\_\_\_\_

Thank you!

**APPENDIX 4: Aboriginal Participant Questionnaire: Hospital Services**

**Tell us what you think about...**

**Being in hospital and then coming home**

**Tick the box you think is right for you...**

	Yes – it was good 	In the middle 	No – it was not good 
Looking back... how I was looked after in hospital			
How staff yarned with me and answered my questions			
How staff talked with my family			
How staff planned for what I wanted when I left hospital			
Receiving the information I needed			
Getting therapy if I needed it			
Preparing me for keeping busy and seeing friends			

**Anything else you want to add?**

---

---

---

---

---

---

---

---

[figure not shown]
**Thank you for telling us how it has been for you.**

**APPENDIX 5: Aboriginal Participant Questionnaire: Aboriginal Brain Injury Coordinator Service**

**Tell us what you think about...**

**Being with your *Aboriginal Brain Injury Coordinator***

Tick the box you think is right for you...

	Yes – I agree. Good 	In the middle 	No – I don't agree. Not good 
This person has helped me understand what was going on while I was in hospital			
This person has helped me get what I needed when I left hospital			
This person has helped my recovery			
This person has helped my family			

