electronic or digital signature or verbally. In the latter scenario the baseline assessor will read aloud information from the Participant Information and Consent Form to provide the patient with project information. The patient's verbal decision will be recorded in the CRF at the recruiting hospital. The patient will then be sent a copy of the study's information sheet. In the case of the investigator not having had the opportunity to approach the person whilst in hospital, the investigator will telephone them, to see if they would be interested in hearing more about the project/being involved. If the person agrees for their name to be given to the clinical trial team, the baseline assessor will then see the person at their home, mutually agreed location or will contact via telephone/telehealth facility in order to further discuss the project, obtain informed consent, and complete the baseline assessment and processes will proceed as above. The informed consent process will involve the use of 'aphasia friendly' information to accommodate patients with communication disorders, those with other cognitive issues typically associated with brain injury, and those with limited literacy skills. The process will also involve a relevant interpreter as needed. In the case of patients with a decision making disability who are incapable of providing consent, we will apply a Research Decision Maker consent pathway. Within this study, exclusion on the basis of inability to give consent would discriminate against individuals with severe brain injury, as the intervention provides additional client and family support and monitoring, rather than being a specific activity based or pharmaceutical intervention.

Participants can be recruited to the study at any time within six weeks post injury.

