As part of the process evaluation, a brief questionnaire will be completed with the assistance of the assessor, focusing on hospital experiences and brain injury related services to date. Another questionnaire surrounding the services of the ABIC as relevant to the intervention period will also be administered. However in order to maintain blinding of the main assessor, another independent assessor will administer this questionnaire

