#### **11.1.2 Aboriginal Brain Injury Coordinator**

An Aboriginal person will be employed for one day/week at each of the project sites as an Aboriginal Brain Injury Coordinator (ABIC). The ABIC will see the participants in hospital and up till 26 weeks post injury onset and provide

education, support, liaison, and advocacy services to the participants and their families.

A minimum qualification of a Certificate 3 in a relevant health or community care subject of study will be required. Qualifications and experiences as an Enrolled or Registered Nurse or in Aboriginal Health Work will be highly desirable.

The ABIC will receive 12 hours of training from the Neurological Council of Western Australia (NCWA) and the research team. Each ABIC will be located either in the hospital, the local community controlled Aboriginal Medical Service (AMS), or offices of the NCWA as part of their community neurological nursing service, depending on the preference of each site. This person will be supported by the local AMS, the NCWA community nursing service, and the research project manager.

The ABIC will visit the person if admitted locally to hospital, and follow up with the person and their family at home/aged care facility for 26 weeks thereafter. In cases of transfer between sites in the study, the ABIC at the site of recruitment will be the primary contact with the participant. Follow up of participants will occur through phone or telehealth contact as agreed upon. However, if the ABIC services have commenced at the place to which the participant is transferred, then the local ABIC will see the participant there. Conversely, if there is no ABIC service at the site of recruitment, the participant will not receive ABIC services even if they are transferred to a hospital region where ABIC services have been introduced, as they are technically part of the control period of the original site.

Further detail of the ABIC's role is outlined in the Intervention Protocol.

Any deviation from the prescribed protocols will be reported as a protocol deviation.

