### **11.2.2 Aboriginal Brain Injury Coordinator**

The activities of the Aboriginal Brain Injury Coordinator that involve direct and indirect contact with participants will be recorded in the e-CRF.

Details to be recorded include: the date of the activity; nature (direct or indirect); modality of direct contact (in-person; telephone; video-conference); location of the participant during contacts; location of ABIC during contacts; the specific activities that occurred (assessment of needs; counselling; goal setting; attending appointments with participant; education to patient and family; making referrals, advocacy, liaison with social services; attendance at multi-disciplinary meetings; consultation with healthcare providers). When the

activity relates to direct participant contact, either face to face or via telephone/video-conference the length of the session should be recorded.

The ABIC will also make clinical notes relevant to care coordination activities with the participant in a participant specific file that is identified by a participant number and which will be kept in a locked cabinet at the ABIC's workplace (either the offices of the NCWA or the Aboriginal Medical Service). These files will also contain an action plan; documented goals; documents related to referrals made; written correspondence with health and support services. The contents of these files will be sent to the recruiting site for storage in the CRF at the recruiting site, at completion of the intervention period.

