**Anything else you want to add?**

---

---

---

---

---

---

---

---

---

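### Item 1 of the coordinator questionnaire (Appendix 5) has no box for intervention-period participants without in-hospital coordinator contact, so it mixes reach with acceptability

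*Protocol*

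**What the plan says.** Appendix 5 is a four-item form on the coordinator service. Item 1 asks whether this person helped the participant understand "what was going on while I was in hospital". Each item has three boxes, and the lowest is labelled "No – I don't agree. Not good". No box covers an item that does not apply. An open comment field ("Anything else you want to add") follows the grid.

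Section 10.2.2 limits who receives the form: "Another questionnaire surrounding the services of the ABIC as relevant to the intervention period will also be administered". Section 10.2.3 repeats this for week 26. In both places an independent assessor administers it, so that the main assessor stays blinded.

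On contact in hospital, the synopsis describes a meeting during the stay as the norm. Section 11.1.2 makes it conditional: "The ABIC will visit the person if admitted locally to hospital". The coordinator is employed one day a week, and after a transfer between sites follow-up may be by phone or telehealth. Section 9 allows recruitment up to six weeks after injury, including after discharge; one of its routes begins "In the case of the investigator not having had the opportunity to approach the person whilst in hospital".

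Section 11.2.2 has the eCRF record, for each coordinator activity, the date, the mode of contact and the "location of the participant during contacts". No section says how a tick or a blank on Appendix 5 is to be scored.

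**The concern.** The item asks about help in relation to the hospital stay, while the protocol admits intervention-period participants whom the coordinator never met or called during that stay. Such a person has three choices: tick a box that also means the service was not good, tick the middle, or leave a blank. None of these records that there was no contact.

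What is at stake is the reading of H6, which states that the package is acceptable to participants and that the coordinator role is feasible. Whether the coordinator reached people in hospital is a question of feasibility. Whether those reached found the help useful is a question of acceptability. Item 1 returns one answer to both. Apart from ten interviews (Section 12.2), this form is the participants' only planned rating of the coordinator, and item 1 is one of its four items.

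**Working it through.** The protocol states no figure for this point, so there is nothing to reproduce. The check sets the form against the routes into the trial.

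1. **Who is asked.** Intervention-period participants only (Sections 10.2.2 and 10.2.3). Control-period participants, who have no coordinator, are not asked.
2. **Who among them may have had no in-hospital contact.**
   - *Recruited after discharge* (Section 9). This is the clearest route and is enough by itself.
   - *Not admitted locally, or transferred* (Section 11.1.2). This route is weaker. A phone call can reach an inpatient, and where the service has started at the receiving site the local coordinator sees the participant.
   - *Short stay missing a one-day-a-week worker* (Sections 11 and 11.1.2). This is a matter of chance. Assume one fixed weekday and arrivals spread evenly over the week. A remaining stay of L days then contains that day with probability min(1, L/7): 2/7 = 29%, 4/7 = 57% and 6/7 = 86% for 2, 4 and 6 days, and 100% from 7 days on. The protocol gives no length of stay and does not say that the day is fixed.
3. **What they can tick.** Agree, middle or the lowest box, or nothing. The lowest box fits both no contact and unhelpful contact. A blank fits both an inapplicable item and a missed one.
4. **Comparison with the protocol's own staff forms.** The usefulness and impact grids in Appendices 2 and 3 carry a further column for other answers, tied to a comment space. The participant form has the comment space but no such column.

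**Illustration on assumed values.** Let a be the agreement among those with in-hospital contact, f the share of respondents without it, and b the share of the latter who leave the item blank, the rest ticking the lowest box. Agreement among those who answer the item is

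a(1 − f) / (1 − f·b).

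With a = 80%:

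| f | b = 0 | b = 0.5 | b = 1 |
|---|---|---|---|
| 10% | 0.72/1 = 72% | 0.72/0.95 = 76% | 0.72/0.90 = 80% |
| 20% | 0.64/1 = 64% | 0.64/0.90 = 71% | 0.64/0.80 = 80% |
| 30% | 0.56/1 = 56% | 0.56/0.85 = 66% | 0.56/0.70 = 80% |

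The distortion runs from none (all blank, or f = 0) to f × 80 percentage points (none blank). The values of a, f and b are all assumptions. Anyone to whom the coordinator explained the stay afterwards may properly tick agree, which reduces the distortion further.

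**The case against.** The case on the other side is substantial.

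- **The form is not given to everyone.** A reader of Appendix 5 alone might infer that all trial participants must answer it. Sections 10.2.2 and 10.2.3 do not support that.
- **Nothing says that these participants are counted as dissatisfied.** A reader might infer it from the label on the lowest box, but no scoring rule, pooling of items or denominator is stated, and such rules may sit in an analysis plan. This stands. The ambiguity nevertheless arises when the box is ticked. An analysis plan can choose a denominator but cannot add a box to completed forms.
- **Item 1 does not strictly require a visit.** A coordinator could help by phone during the stay, or explain it after discharge. This stands, and it argues against limiting the item to people with a logged in-hospital contact, since that would drop anyone helped later.
- **There are safeguards.** An assessor administers the form, comments are possible, ten participants are interviewed, and the contact log is monitored monthly. These help. But no instruction tells the assessor how to handle an inapplicable item, and free text is hard to tabulate and hard to use for participants with communication or literacy difficulties. The log shows who was reached, not what a given tick meant.
- **Appendix 4 might seem to share the fault.** The argument is weak there. "Getting therapy if I needed it" already carries its own condition, and staff can talk with a family that is not present: Section 10.4 counts telephone contact with family. The point is confined to Appendix 5.
- **Three boxes may be a deliberate simplification** for this population. That is a fair reason to add no more than one.

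**Conclusion.** The point holds as a minor fault in the instrument. For intervention-period participants without in-hospital contact, a tick in the lowest box on item 1 cannot be separated from dissatisfaction, nor a blank from a missed item, so the item mixes reach with acceptability.

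Its size cannot be derived from the protocol. It is negligible if such participants are few, and agreement among those answering is undistorted if they all leave the item blank. It grows in proportion to their number if they tick the lowest box. A reader might take the lower figures in the table as a forecast of understated acceptability. They are not, because they rest on an assumed share and an assumed way of answering.

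Only one of four items on a descriptive process-evaluation form is affected. The EQ-5D-3L VAS analysis, the sample size and the error rates are untouched.

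**What to change.** - Add one box to Appendix 5: does not apply / did not see this person then. Tell the assessor to offer it.
- Report item 1 among those who did not tick that box, and give the number who did.
- Show item 1 split by whether the eCRF logs a coordinator contact while the participant was in hospital. Keep both groups rather than excluding those without such a contact.
- Report the share with no logged contact during the stay separately, as a measure of reach.

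The cost is one more box on a deliberately simple form, slightly smaller item denominators, and one short tabulation from fields that the eCRF already holds. For forms already completed without the box, the split by logged contact can still be made, but the meaning of individual ticks and blanks cannot be recovered.

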**Anything else you want to add?**

---

---

---

---

---

---

---

---

---

**Thank you for telling us how it has been for you.**

## **APPENDIX 6: Aboriginal Brain Injury Coordinator Interview Schedule**

### **Topics and related questions for semi-structured interview for the Aboriginal Brain Injury Coordinators**

- Tell us a little about your role in this project.
  - What did you do?
- What did you think about your training?
  - Did you get enough training?
  - What was the most beneficial aspect of your training?/ Comment on the usefulness or relevance of a) orientation b) training c) clinical supervision
  - Is there information/ training you feel would have been useful to receive to help you in your ABIC role? If so, what additional information/ training would you have liked to receive?
- Did the role meet your expectations of what it would be?
- What things, if any, helped you achieve what you wanted to do in your role?
- What things, if any, got in the way of your ability to achieve what you wanted to do in your role?
- Do you feel you were able to help your participants to access rehabilitation services?
  - If so, how did you help them? What did you do that made a difference to them?
  - If not, what were the main things that prevented this?
- What parts of the ABIC service did you feel the participant found the most useful?
- How would you explain your role to someone outside of the project?
- What advice would you give to a service that was looking to employ Aboriginal Brain Injury Coordinators?
- What was your experience of being based at the Neurological Council of WA/Aboriginal Medical Service? Can you comment on:
  - your ability to perform your role in a way that reflected the needs of your Aboriginal participants
  - your own feelings of cultural safety in the workplace
  - what you think makes a workplace feel comfortable for Aboriginal staff
- What was your experience of working with the staff at the hospital e.g. medical team, ALOs, allied health team?
- What was your most memorable moment during your work as a Brain Injury Coordinator?
- Do you have anything you'd like to add/share?
